13.1.4.2 Primary Analysis

For the Double-blind Period only, the number and proportion of subjects in each treatment group with successful resolution of LI by Day 90/EOT will be presented. The primary efficacy endpoint will be analyzed using a logistic regression model with treatment and age group as factors. Other baseline characteristics and interactions may be included. The odds ratios and 95% CIs for the odds ratios will be presented. The difference in proportions between the active trifarotene cream HE1 and vehicle cream group, 95% CIs for the differences, and P-values for the differences in treatment will also be presented.

Descriptive summaries (such as mean, standard error, median, minimum, and maximum) and the changes from baseline will be provided for IGA scores for both periods.

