8.2. Study Entry Criteria

8.2.1 Inclusion Criteria

A subject will be eligible for study participation if he or she meets all of the following criteria:

1. Subject is ≥ 18 years old.
2. Subject has known diagnosis of LI.
3. Subject has moderate to severe (IGA 3–4) LI on the IGA of LI severity.
4. Subject has signed an ICF at Screening before any investigational procedures.
5. Subject who is participating in optional photography has signed a photography ICF.
6. Subject who is participating in the optional PK substudy has signed a PK ICF.
7. Subject is not of childbearing potential, i.e., a female who is postmenopausal (absence of menstrual bleeding for 1 year before Baseline, without any other medical reason), or has documented hysterectomy, bilateral salpingectomy, or bilateral oophorectomy). For individuals with permanent infertility due to an alternate medical cause other than the above, (e.g., Mullerian agenesis, androgen insensitivity), investigator discretion should be applied to determining study entry.

OR

Subject is a woman of childbearing potential (WOCBP) or a male subject with sexual partners capable of reproduction who agrees to use 2 effective forms of contraception during the study and for at least 1 month after the last study drug application. The 2 authorized forms of contraception are condom used with 1 of the following methods of contraception:

- bilateral tubal ligation

- combined oral contraceptives (estrogens and progesterone), vaginal ring, or implanted or injectable hormonal contraceptives with a stable dose for at least 1 month before Baseline; hormonal contraceptives must inhibit ovulation
- intrauterine device (IUD) inserted at least 1 month before Baseline

OR

Agrees to abstain from heterosexual intercourse during study participation and for 1 month after the last application of study drug and to use a highly effective contraceptive as backup if he or she becomes sexually active during the study. Abstinence is only acceptable if this is the subject's usual lifestyle. Periodic abstinence (calendar, symptothermal, postovulation methods), withdrawal (coitus interruptus), spermicides only, and lactational amenorrhoea method are not acceptable methods of contraception.

AND

Male subjects may not donate sperm during the study and for at least 1 month after the last study drug application.

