9.6. Method of Assigning Subjects to Treatment Groups

In the double-blind, parallel-group, randomized period of the study, subjects who meet study entry criteria will be randomly assigned in a 1:1:1 ratio to trifarotene cream HE1 100 µg/g or 200 µg/g or vehicle cream. The randomization schedule will be computer generated using a permuted block algorithm and will randomly allocate IP to randomization numbers. The randomization numbers will be assigned sequentially through a central interactive web response system (IWRS) as subjects are entered into the study. Study center will not be a blocking factor in the randomization schedule.

Premier Research will prepare the randomization schedule before the start of the study. No one involved in the study performance will have access to the randomization schedule before the official unblinding of treatment assignments. No subject will be randomized into this study more than once.

In the OLE, all subjects will receive trifarotene cream HE1 200 µg/g.

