13.1.4.1 Efficacy Endpoints

Primary efficacy endpoint: The proportion of subjects in each treatment group who experience successful resolution of LI where “success” is defined as clear/almost clear overall and at least a 2-grade change from Baseline at Day 90/EOT in the Double-blind Period on the 5-point IGA scale.

Secondary: The secondary endpoints are as follow:

- The difference in mean scores between the active trifarotene cream HE1 and vehicle groups in the following assessment indices from Baseline through Day 90:
 - 5-point VIIS scale for scaling
 - Individual score for roughness (Scale: 0–4)
 - Palm/sole Assessment (Scale: 0–4)
 - Quality of life per DLQI
- The difference in proportion of subjects with presence of fissures on palm/soles (presence/absence, number of fissures, and pain associated with fissures [on a 0-3 scale]) at Day 90 between the active trifarotene cream HE1 and vehicle groups

Exploratory: The exploratory endpoints are as follow:

- The difference in mean ectropion scores (ESS of 0–8) between the active trifarotene cream HE1 and vehicle groups from Baseline through Day 90
- The difference in quality of life per EQ-5D-5L scores between the active trifarotene cream HE1 and vehicle groups from Baseline through Day 90

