13.1.4.5 Corroborative, Sensitivity, and Other Analyses

To assess the effect of missing data on the primary efficacy analysis, a sensitivity analysis will be performed using multiple imputation (MI) for the Double-blind Period only. Multiple-imputations will be used to replace missing IGA outcomes using multiple draws from the posterior predictive distribution estimated from the treatment groups. IGA scores will be imputed and then categorized as treatment success according to Section 13.1.4.1. Imputation will not be performed for the OLE. Full details will be specified in the SAP.

Thorough assessment on the extent of missing data and procedural adjustments due to COVID-19 as it pertains to the primary and secondary efficacy endpoints will be conducted ahead of database lock, and additional sensitivity analyses may be performed. Full details will be documented in the SAP.

The proportion of subjects who experience a 2-grade change from baseline to Day 90 in individual score for roughness and palm/sole assessment will also be explored using a logistic regression model with treatment and age group as factors. Other baseline characteristics and interactions may be included. The odds ratios and 95% CIs for the odds ratios will be presented. The difference in proportions between the active trifarotene cream HEI and vehicle cream group and the 95% CIs for the differences will be presented.

For analyses involving study site, if the number of subjects per site is small, sites may be pooled for safety and efficacy analysis or omitted from statistical models as the anticipated number of subjects per site is small, treatment is self-administered, and the sites are using standardized procedures for all assessments. If the distribution of enrollments at sites is such that one or few are

enrolling a majority of subjects, a subgroup analysis by site may be performed. The final determination will be made prior to database lock.

Details of these analyses will be further detailed in the SAP.

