
STUDY ENTRY CRITERIA
	
Inclusion criteria:
 
 1. For Cohort A: subject is ≥18 years old; for Cohort B: subject is ≥12 years old. 2. Subject has known diagnosis of LI. 3. Subject has moderate to severe (IGA 3-4) LI on the IGA of LI severity. 4. Subject has signed an ICF at Screening before any investigational procedures. Subjects <18 years of age (or Age of Majority) must sign an assent form in conjunction with an ICF signed by the parent/legal representative. 5. Subject who is participating in photography has signed a photography ICF. 6. Subject who is participating in the optional PK substudy has signed a PK ICF. Minors, in the event of their reaching majority during the study, should be capable of giving consent to take part in the PK substudy. 7. Subject is not of childbearing potential, who is postmenopausal (absence of menstrual bleeding for 1 year before Baseline, without any other medical reason), or has documented hysterectomy, bilateral salpingectomy, or bilateral oophorectomy. For individuals with permanent infertility due to an alternate medical cause other than the above, (e.g., Mullerian agenesis, androgen insensitivity), investigator discretion should be applied to determining study entry. 
OR
 
Subject is a woman of childbearing potential (WOCBP), i.e. a female ≥12 years of age (regardless of whether they have experienced/reported menarche), or a

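### The primary logistic model fixes an undefined age-group factor in the adults-only text and does not name baseline IGA (3 v 4), which sets how far a subject must improve to succeed

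*Protocol*

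**What the plan says.** In the Amendment 3 text, Section 13.1.4.2 states that the primary endpoint will be "analyzed using a logistic regression model with treatment and age group as factors", and the Synopsis (2.1) gives the same model. Section 13.1.4.2 then adds "Other baseline characteristics and interactions may be included", without naming any. Section 13.1.4.3 reuses this model for the 50% IGA-reduction analysis. Section 13.1.4.5 says that 2-grade changes in roughness and palm/sole scores will be "explored using a logistic regression model with treatment and age group as factors".

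On age, Section 8.2.1 of the same text requires "Subject is ≥ 18 years old". The file also holds a second full text, Amendment 2, under the same protocol and EudraCT numbers. Its Synopsis has "for Cohort B: subject is ≥12 years old" and the same model sentence.

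On severity, entry requires "Subject has moderate to severe (IGA 3–4) LI on the IGA of LI severity" (8.2.1). Success is "clear/almost clear overall and at least a 2-grade change from Baseline at Day 90/EOT" (13.1.4.1). IGA score is listed as a baseline characteristic in 13.1.2.3.

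On allocation, Section 9.6 says "The randomization schedule will be computer generated using a permuted block algorithm and will randomly allocate IP to randomization numbers". It rules out study center as a blocking factor and states no stratification by age or severity.

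**The concern.** The model spends its one named covariate on a variable that the adults-only text gives no content. No cut-point appears, no reason for splitting adults by age is given, and age plays no stated part in the randomisation.

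The baseline value tied most directly to the endpoint is left unnamed. The starting grade fixes the distance to success, so baseline IGA is the obvious candidate for a prognostic covariate. The protocol adjusts for the baseline score in its own MMRM for the continuous secondary endpoints (13.1.4.3), but not in the primary analysis.

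Three things are at stake: a primary model left open at protocol level, some precision, and chance severity imbalance that the stated model would leave in the treatment estimate.

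**Working it through.** **Inputs from the documents.** Two-sided 0.05 (13.1); 70% v 40% success, 1:1:1, 120 randomised (40 per arm), 20% drop-out, 32 evaluable per arm (13.2); baseline IGA 3 or 4 (8.2.1); success as in 13.1.4.1.

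**Inputs assumed.** The share of subjects at IGA 4 (30% or 50%) and the odds ratio of success for IGA 4 v 3 (1, 0.5, 0.25, 0.1). The documents give neither.

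**The plan's own figure.** The plan gives no figure for covariate adjustment. Its nearby figure, more than 80% power by two-sided Fisher test at 32 per arm, is not reproduced: exact enumeration gives 61.9%. That is a separate matter, and this point does not rest on it.

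**1. Levels of age group.** On the only split in the file (12–17 v 18 and over), every subject eligible under the Amendment 3 text is in the upper level. A one-level factor equals the intercept and has no estimable coefficient. If subjects from both texts are pooled, it has two levels.

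**2. Distance to success.** The target is IGA 0 or 1. From 3, the smallest sufficient fall is 3 − 1 = 2 grades. From 4, it is 4 − 1 = 3 grades.

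**3. Power.** Simulation with 4,000 trials per scenario, active v vehicle, Wald test of treatment, intercept and treatment effect solved so that the marginal rates stay at 40% and 70%. Ranges cover the two assumed IGA 4 shares.

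| Assumed success OR, IGA 4 v 3 | 32/arm: without → with baseline IGA | 40/arm: without → with baseline IGA | Treatment OR given baseline IGA |
|---|---|---|---|
| 1 | 0.70–0.73 → 0.69–0.71 | 0.80 → 0.78–0.79 | 3.5 |
| 0.5 | 0.71–0.72 → 0.70 | 0.79–0.80 → 0.78–0.79 | 3.6 |
| 0.25 | 0.71–0.72 → 0.72 | 0.79–0.80 → 0.80–0.82 | 4.0–4.1 |
| 0.1 | 0.71–0.72 → 0.76–0.78 | 0.80 → 0.86–0.87 | 5.0–5.3 |

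Within scenarios, the change runs from 0.710 − 0.733 = −0.02 to 0.868 − 0.803 = +0.06.

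**4. Chance imbalance.** With independent binomial draws and a 30–50% share at IGA 4, two arms differ by 15 points or more in that share with probability about 22–26% at 32 per arm and 18–22% at 40 per arm. With half at IGA 4, the calibrated vehicle success rates (IGA 3, IGA 4) are 0.48 and 0.32 at OR 0.5, 0.56 and 0.24 at OR 0.25, and 0.65 and 0.15 at OR 0.1. A 15-point difference in mix then moves the expected vehicle rate by:

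- 0.15 × 0.16 = 2.4 points (OR 0.5)
- 0.15 × 0.32 = 4.8 points (OR 0.25)
- 0.15 × 0.50 = 7.5 points (OR 0.1)

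The planned difference is 30 points.

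**5. Scale of the odds ratio.** The marginal odds ratio is (0.7/0.3) ÷ (0.4/0.6) = 3.5. The last column of the table shows that the odds ratio given baseline IGA is a different, larger quantity when baseline IGA is prognostic, although the marginal rates are unchanged.

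**The case against.** **The versions may be pooled.** This stands, and it limits the fix. Both texts plan about 120 subjects, 15 plus 105. Both change logs start from the same 12-week base text, and the 25 reasons listed for Amendment 3 do not include removing adolescents. The two may be parallel versions of one trial, though the documents do not say so. A reader might infer that age group is simply a leftover to strike out. The file does not establish that, and under pooling age group would be a proper two-level factor.

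**The SAP will settle the details.** This stands in part. Section 13.1 calls itself a summary, and a cut-point or a covariate list can be left to the SAP. But here the protocol positively names a factor that its own entry criterion leaves with one level on the only split given. Without pooling, a SAP could only introduce a new split or depart from the protocol.

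**Baseline IGA is not excluded.** Correct. It is a listed baseline characteristic, and the open clause allows it. It is unnamed, not forbidden.

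**The primary analysis is not broken.** Correct. A reader might infer that the model cannot be fitted or that the test is invalid. A one-level factor is ordinarily dropped and the treatment estimate is unchanged. Leaving a prognostic covariate out of a randomised comparison does not inflate type I error.

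**The gain is small.** Also correct. It is clearly visible only at the strongest assumed severity effect.

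**Conclusion.** The point holds as one of specification and efficiency. In the adults-only text, age group is an undefined factor that adjusts for nothing unless the two versions are pooled. Baseline IGA, which sets a 2-grade or a 3-grade requirement, is left to an open clause.

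Naming baseline IGA is worth about −2 to +6 points of power. That range rests on assumed severity odds ratios from 1 to 0.1 and assumed IGA 4 shares of 30–50%. Naming it also corrects a chance severity imbalance of 15 points or more, which has a probability of roughly one in five to one in four.

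There are two small downsides. About 2 points of power are lost if baseline IGA is not prognostic, and the adjusted odds ratio is conditional, so it cannot be read as the marginal one. The documents do not support saying that the primary test is invalid, that type I error is inflated, or that power suffers greatly.

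**What to change.** - In the Synopsis (2.1) and Section 13.1.4.2, make the primary model success on treatment plus baseline IGA (3 v 4), and put this in place of the clause on other baseline characteristics and interactions. The 50% IGA-reduction analysis in 13.1.4.3 follows by cross-reference.
- State whether subjects enrolled under the two texts will be analysed together. If so, keep age group as an explicit 12–17 v 18-and-over factor. If not, delete it.
- For each dose v vehicle, report the adjusted odds ratio and, beside it, the risk difference standardised to the trial's baseline IGA distribution, each with a 95% CI.
- In Section 13.1.4.5, adjust each responder model for its own baseline score (roughness or palm/sole), and treat age group as above.

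The cost is wording in the protocol and the SAP, settled before unblinding. Baseline IGA and the other two scores are already recorded at Baseline.

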13.1.4.3 Secondary Analyses

Secondary and exploratory efficacy endpoints will be analyzed separately for each period (Double-blind and OLE) using descriptive statistics.

Additionally, for the Double-blind Period only, change from Baseline in continuous secondary endpoints through Day 90 will be presented and analyzed using a mixed model for repeated measures (MMRM). The model will include the change from baseline score as the dependent variable, treatment group as a fixed effect, subject as a random effect, and baseline score value as a covariate.

For subjects who report having fissures, descriptive summaries of the number of fissures and pain related to fissures will also be presented by treatment group and body area for each period.

The DLQI scores will also be analyzed using descriptive statistics through Day 90.

The proportion of subjects with at least a 50% reduction in IGA score from Baseline will be analyzed using the same logistic regression analysis described in Section 13.1.4.2.

13.1.4.4 Exploratory Analyses

Descriptive summaries and the changes from baseline will be provided for ectropion scores and EQ-5D-5L scores by visit for each period. No formal inferential analyses will be conducted for exploratory endpoints.

13.1.4.5 Corroborative, Sensitivity, and Other Analyses

To assess the effect of missing data on the primary efficacy analysis, a sensitivity analysis will be performed using multiple imputation (MI) for the Double-blind Period only. Multiple-imputations will be used to replace missing IGA outcomes using multiple draws from the posterior predictive distribution estimated from the treatment groups. IGA scores will be imputed and then categorized as treatment success according to Section 13.1.4.1. Imputation will not be performed for the OLE. Full details will be specified in the SAP.

Thorough assessment on the extent of missing data and procedural adjustments due to COVID-19 as it pertains to the primary and secondary efficacy endpoints will be conducted ahead of database lock, and additional sensitivity analyses may be performed. Full details will be documented in the SAP.

The proportion of subjects who experience a 2-grade change from baseline to Day 90 in individual score for roughness and palm/sole assessment will also be explored using a logistic regression model with treatment and age group as factors. Other baseline characteristics and interactions may be included. The odds ratios and 95% CIs for the odds ratios will be presented. The difference in proportions between the active trifarotene cream HEI and vehicle cream group and the 95% CIs for the differences will be presented.

For analyses involving study site, if the number of subjects per site is small, sites may be pooled for safety and efficacy analysis or omitted from statistical models as the anticipated number of subjects per site is small, treatment is self-administered, and the sites are using standardized procedures for all assessments. If the distribution of enrollments at sites is such that one or few are

enrolling a majority of subjects, a subgroup analysis by site may be performed. The final determination will be made prior to database lock.

Details of these analyses will be further detailed in the SAP.

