13. STATISTICS

13.1. Statistical Analysis

This section presents a summary of the planned statistical analyses. A SAP that describes the details of the analyses to be conducted will be written prior to database lock.

Unless otherwise indicated, all testing of statistical significance will be two-sided, and a difference resulting in a P value of ≤ 0.05 will be considered statistically significant.

Summary statistics will be provided for the variables described below. For continuous variables, these statistics will include the number of subjects, mean, standard deviation (SD), median, minimum, and maximum. For categorical variables, these statistics will include the number and percentage of subjects in each category.

The primary analysis period is the first 90 days of treatment (i.e., the Double-blind Period). Overall unblinding will take place at the end of the Double-blind Period of the study only after the database is locked. A second analysis will take place for endpoints assessed from Day 90 through the OLE

Period. The baseline for the safety and efficacy parameters will be measured at Visit 1 or Visit 2, per the Schedule of Events for both the Double-blind Period ([Table 2-1](#)) and OLE ([Table 2-2](#)).

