13.1.1 Analysis Populations

The following 5 analysis populations are planned for the Double-blind Period of this study:

- Safety: all subjects who are randomized to treatment and receive at least 1 application of study drug in the Double-blind Period. This population will be the primary population for analyses of safety.
- Intent-to-treat (ITT): all randomized subjects. This population will be used as the primary population for the analysis of efficacy for the Double-blind Period of the study.
- Modified intent-to-treat (mITT): all subjects in the safety population with at least 1 postbaseline assessment of efficacy in the Double-blind Period.
- Per-protocol (PP): subjects in the mITT Population who met all inclusion criteria and no exclusion criteria, were compliant with study drug application, and who had no significant protocol deviations.
- Pharmacokinetic: all subjects in the Safety Population who have at least 1 plasma sample with quantifiable concentration. This population will be used to summarize all PK endpoints.

The following analysis populations are planned for the OLE of this study:

- OLE Safety: all subjects who complete the 90-day Double-blind Treatment Period and receive at least 1 application of study drug in the OLE.
- OLE ITT: all subjects who complete the 90-day Double-blind Treatment Period and sign the OLE informed consent.
- OLE mITT: all subjects in the OLE safety population with at least 1 assessment of efficacy after Visit 6.
- OLE PP: all subjects in the OLE mITT population who met all inclusion criteria and no exclusion criteria, were compliant with study drug application from baseline through EOT, and who had no significant protocol deviations throughout the study.

Inclusion in the analysis populations will be determined prior to database lock. Deviations related to COVID-19 will also be evaluated in determining PP population eligibility.

If a subject is randomized incorrectly or is administered the incorrect IP, analyses of the ITT and mITT populations will be based on the assigned treatment whereas all other analyses will be based on the actual treatment received.

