13.2. Sample Size Determination

Accounting for a 20% drop-out/nonevaluable rate, a total sample size of 120 subjects randomized in a 1:1:1 ratio to 2 active trifarotene cream HE1 arms and a vehicle cream arm will provide >80% power to detect a difference between each separate trifarotene cream HE1 arm (32 evaluable subjects) and the vehicle cream arm (32 evaluable subjects) 2-sided Fisher's Exact Test assuming a 70% success rate and a 40% success rate, respectively. This study is not powered to detect a difference between the 2 active arms.

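### The only missing-data analysis that Section 13.1.4.5 commits to assumes missing-at-random, so it cannot show whether the primary result survives outcome-related dropout

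*Protocol*

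**What the plan says.** Protocol 13.1.1 defines ITT as everyone randomized and says of it: "This population will be used as the primary population for the analysis of efficacy for the Double-blind Period of the study". Section 13.1.4.2 gives the primary model: "The primary efficacy endpoint will be analyzed using a logistic regression model with treatment and age group as factors". Section 13.1.4.1 reads success at Day 90 or end of treatment.

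Section 13.1.4.5 introduces its sensitivity analysis as a way to assess the effect of missing data on the primary analysis. Multiple imputation will "replace missing IGA outcomes using multiple draws from the posterior predictive distribution estimated from the treatment groups", and the imputed IGA scores are then classified as success or not. Details go to the SAP. After a pre-lock review of missing data and COVID-19 adjustments, further sensitivity analyses are allowed but not required, and no method is named for them.

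Section 13.2 sets the scale of expected loss: "Accounting for a 20% drop-out/nonevaluable rate, a total sample size of 120 subjects randomized in a 1:1:1 ratio", with 32 evaluable subjects per arm.

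**The concern.** A sensitivity analysis for missing data is useful when it changes the assumption about the unseen outcomes. Imputing from the subject's own arm assumes that, given what the model conditions on, those who left would have succeeded as often as those who stayed.

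The protocol gives reasons to doubt this. Section 8.3 lets the investigator withdraw subjects for lack of therapeutic effect or unacceptable adverse events. Section 5.3 lists application-site irritation as an expected effect of the active drug. Section 5.2 reports that irritation forced a cut in application frequency in healthy volunteers. Dropout could therefore be related to outcome and differ between trifarotene and vehicle.

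If the one committed analysis shares the assumption under question, its agreement with the primary result says little about robustness. A positive finding that depended on the unseen outcomes could be reported as confirmed.

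**Working it through.** **Inputs.** From 13.2: 120 subjects, 1:1:1, 20% drop-out or nonevaluable, success 70% on active and 40% on vehicle. From 13.1: two-sided testing at 0.05. Assumed for illustration: the whole 20% lack an IGA score.

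**The plan's own count.** 120/3 = 40 per arm; 40 × 0.8 = 32 evaluable; 8 not evaluable. This reproduces. (The stated power above 80% does not: exact two-sided Fisher power at 32 per arm is 61.9%. That is a separate matter.)

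**Expected difference.** Let a and b be the missing fractions on active and vehicle, and s_A and s_V the success rates assumed for the missing:

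D = [(1 − a) × 0.70 + a × s_A] − [(1 − b) × 0.40 + b × s_V]

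- Own-arm imputation, arm-only model: s_A = 0.70 and s_V = 0.40, so D = 0.70 − 0.40 = 30 points whatever a and b are.
- All missing fail, a = b = 0.20: 0.56 − 0.32 = 24 points.
- Missing active subjects given the vehicle rate, a = b = 0.20: (0.56 + 0.20 × 0.40) − 0.40 = 0.64 − 0.40 = 24 points.
- All missing fail, a = 0.30 and b = 0.10 (assumed): 0.49 − 0.36 = 13 points.
- All missing fail, a = 0.10 and b = 0.30 (assumed): 0.63 − 0.28 = 35 points.

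The arm-only imputation does not respond to any of these scenarios.

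**Whole-number illustration**, counts chosen near the planned rates, 8 missing per arm:

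| Handling of the missing | Active | Vehicle | Difference (points) | Fisher p |
|---|---|---|---|---|
| Observed cases | 22/32 = 68.8% | 13/32 = 40.6% | 28.1 | 0.044 |
| Own-arm imputation (beta-binomial, 5000 draws, Rubin's rules) | – | – | 28.1 | – |
| All missing fail | 22/40 = 55.0% | 13/40 = 32.5% | 22.5 | 0.071 |
| Missing active given the vehicle rate | (22 + 3.25)/40 = 63.1% | 40.6% | 22.5 | – |

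Here 3.25 = 8 × 13/32. The observed-case standard error is √(0.6875 × 0.3125/32 + 0.40625 × 0.59375/32) = 0.119, and the imputation's combined standard error is also 0.119. Both the estimate and its precision are returned unchanged.

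**What a tipping-point table would span.** With the same counts, the corners run from 22/40 v (13 + 8)/40 = 55.0% v 52.5%, or 2.5 points, to (22 + 8)/40 v 13/40 = 75.0% v 32.5%, or 42.5 points. The analysis named in 13.1.4.5 explores none of this range.

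**The case against.** **The 20% is not a missing-IGA rate.** A reader might infer that a fifth of each arm will have no Day 90 IGA. Section 13.2 calls it a drop-out or nonevaluable rate. Footnote b to Table 2-1 and Section 10.2.2.7 give early terminators the Day 90 procedures, including the IGA, and the endpoint may be read at end of treatment. Subjects with irritation can also reduce or pause application under 9.4 without leaving. This stands, and makes the figures above an upper case.

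**ITT in name, completers in fact.** A reader might also infer that the primary model drops subjects without an IGA. The protocol does not say so. It is silent on their scoring, and the rule may properly sit in the SAP, which is not shown. That reading is not supported.

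**Imputation need not repeat the observed cases.** The wording suggests own-arm imputation but does not spell it out. IGA is recorded at Baseline and Days 14, 30, 60 and 90, and a model using those visits could give poorer scores to subjects who were doing poorly. This stands against any claim that the two analyses must agree. It does not remove the point, because such a model still assumes missing-at-random.

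**Further analyses are possible.** They are, but as an option without a method. A committed analysis would be more useful than a permitted one.

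**Large bias figures are conditional.** Suppose true success is 36% in both arms, dropout is 30% on active and 10% on vehicle, every drop-out fails and none has an exit IGA. Observed-case rates are then 0.36/0.70 = 51.4% and 0.36/0.90 = 40.0%, a bias of 11.4 points, and active is wrongly favoured in 12.8% of trials by Fisher's test (14.3% by a z-test). If half the drop-outs have an exit IGA, scored as failure, the rates are 0.36/0.85 = 42.4% and 0.36/0.95 = 37.9%, a bias of 4.5 points, and the Fisher figure is 4.1%. With equal 20% dropout there is no bias under the null. The split is assumed, and the reverse split works the other way.

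**Conclusion.** The point holds for the choice of sensitivity method. Section 13.1.4.5 sets out to assess the effect of missing data and commits only to an analysis that, on its natural reading, keeps the missing-at-random assumption. If 20% per arm had no score and all failed, the difference would fall from 30 to 24 points at the planned rates, or from 28.1 to 22.5 points in the illustration, where p moves from 0.044 to 0.071. An arm-only imputation would show none of that. The counts are illustrative and deliberately near the significance boundary. The true gap depends on how many exit IGAs are obtained and on how dropout splits by arm, neither of which the protocol gives.

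The documents do not support going further and requiring non-success as the primary rule. Appendix B allows remote visits; without video, only better, worse or unchanged is recorded, so some IGAs may be missing for logistical reasons. Counting those as failures is a trade-off, not the correction of an error. This is a worthwhile, inexpensive improvement and not a flaw that invalidates the primary analysis.

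**What to change.** In 13.1.4.5:

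- Keep the multiple imputation, labelled as supportive and as a missing-at-random analysis.
- Commit to at least one analysis that departs from missing-at-random for subjects without a Day 90/EOT IGA. It can be a tipping-point table over the success rate assumed for missing subjects in each arm, vehicle-based imputation for trifarotene subjects who stopped for an adverse event or lack of effect, or both. Show missing as non-success as one point of the table.
- Handle separately the IGAs that are missing only because a visit was remote without video.

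The cost is protocol and SAP wording and a few extra programs, with no change to data collection. The downside is that the robustness statement may come out less favourable than under the imputation alone.
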